Participants will attend an orientation session via Zoom or in person to introduce them to mindfulness, smoking cessation, and what is covered in the group sessions. This orientation will last 60-90 minutes. They will receive twice weekly group sessions (eight total during 4 weeks) via Zoom or in person that were manualized and will be delivered in Spanish or English by a Hispanic instructor(s) experienced in MT (a single therapist with >4 years of training in MT). We will e-mail participants study materials ahead of the first group session, such as the participant study booklet. We will also communicate with participants using WhatsApp to send them reminders and links to mindfulness recordings.

The overarching theme of momentary awareness and acceptance of cravings and affect (e.g., stress, anxiety etc.) will be introduced and reinforced in complementary ways throughout the training. Each session will last 45-60 minutes.

- a. *Session (1):* Will introduce participants to the concept of how smoking can become a habituated behavior triggered by an environmental, physical, or mental stimulus through associative learning. It also will explore how cravings feel in the body and how MT can help individuals become more aware of these processes.
- b. *Session (2):* Will examine how thoughts, emotions and body sensations become triggers for craving and smoking and introduce a technique to ‘mindfully’ work with cravings (Recognize, Accept, Investigate and Note what cravings feel like as they arise; acronym: RAIN).
- c. *Session (3):* Will introduce how difficult emotions perpetuate smoking as well as a standard meditation technique called loving-kindness as a way to work with them. Loving-kindness is practiced through directed well wishing, typically by repetition of phrases such as ‘may X be happy.’
- d. *Session (4) (quit date):* Will teach participants how cravings thwart long-term goals, and reinforce mindfulness techniques as a way to help individuals disengage from habitual responding and realign with their goals.
- e. *Session (5):* Will introduce participants to mindfulness practice in everyday life, including “awareness of breath” meditation and mindful walking (“four modes of walking”), during which individuals practice systematically noting

objects that they see, and then objects that they hear, then objects that they smell, and then tactile objects such as the pressure of their feet on the ground).

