All study data will be entered and captured by REDCap, which provides secure data capture for clinical and non-clinical research studies.

8) Risks to Subjects*

The risks to subjects, immediate and long range, are considered minimal. Study participants will be asked to complete questionnaires before and after receiving advice to quit smoking, either self-help materials to quit or a behavioral intervention, as well as nicotine replacement for smoking cessation. It is possible that subjects might become psychologically distressed while completing the questionnaires or be dissatisfied with the self-help information or intervention. They will be provided with transdermal nicotine patches that are available over-the-counter. Participants will be required to indicate whether they have any health conditions that may negatively interact with the patches.

To minimize the risk of psychological distress due to questionnaire completion, the measures do not contain private or potentially embarrassing items, and will take about 30-45 minutes for completion time per assessment. To minimize the risk of dissatisfaction with the intervention, we will use an established intervention that has high efficacy. To minimize risks associated with the nicotine patches, subjects will be provided with thorough education of the indications for the nicotine patch, possible side effects, and known health conditions that preclude patch use. The patches are available over the counter; thus, they do not pose a significant health risk to most people. They contain minimal amounts of nicotine (which are much less than they get from smoking), and are absent the remaining 7,000 toxins contained in cigarettes. In addition, we will refer patients with a questionable medical history to their physician or to Jackson Memorial Hospital for consultation.

Though we regard the risks of participating in this study as low, we will take every measure to ensure that every recruiter, interviewer or project personnel, is trained to handle situations sensitively and with empathy. All research staff are required to complete site mandated training on the Protection of Human Research Participants.

9) Adverse Events (AE) and Serious Adverse Events (SAE)

Adverse events for this study may include the following:

EXPECTED:

- a. Symptoms of nicotine withdrawal, such as headaches, cravings, insomnia, anxiety, or depression.

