- b. Side effects of using the nicotine replacement patches, such as minor skin irritation or rash).

These expected AE will be recorded in the participant tracking database. Participants will be advised to review the materials they received on nicotine withdrawal and proper use of NRT patches. If unmanageable symptoms persist of withdrawal or NRT use

persis, participants will be advised to discontinue use of NRT and see their physician.

UNEXPECTED

- c. Unexpected negative psychological reactions to practicing mindfulness.

These unexpected AE will also be recorded in the participant tracking database. If negative reactions to the mindfulness practice cannot be resolved within the group session by the trained mindfulness expert, participants will be advised see their physician. If severe reactions occur and cannot be resolved, study staff will call 911. We do not expect this SAE to occur, nor are any other SAE anticipated.

10) Potential Benefits to Subjects*

Individual subjects can potentially benefit from participating in the study because they will have the opportunity to make a quit attempt and the possibility of long-term smoking cessation. This is associated with a number of additional benefits including improved health, economic savings, the confidence and happiness associated with becoming an ex-smoker, and reducing their stress as a result to practicing mindfulness.

11) Vulnerable Populations*

This research study does not include vulnerable populations.

12) Setting

The primary study site is the University of Miami Miller School of Medicine Campus. Recruitment will mostly take place at UHealth and community clinics, social media (e.g., Facebook), and organizations serving people living with HIV. The consent process, participant assessments, and group meetings will take place via Zoom.

13) Resources Available

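### Adverse events are sorted by presumed cause with no attribution rule and no tabulation by arm, so psychological reactions to mindfulness training may be under-counted

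*Combined protocol and SAP*

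**What the plan says.** Section 9 (Adverse Events and Serious Adverse Events) gives three categories, each defined by a cause.

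- (a) Expected, withdrawal: "Symptoms of nicotine withdrawal, such as headaches, cravings, insomnia, anxiety, or depression".
- (b) Expected, patch: "Side effects of using the nicotine replacement patches, such as minor skin irritation or rash".
- (c) Unexpected, mindfulness: "Unexpected negative psychological reactions to practicing mindfulness". No symptoms are listed.

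Both classes go to the same place: "These expected AE will be recorded in the participant tracking database" and "These unexpected AE will also be recorded in the participant tracking database". Follow-up depends on the label. For expected events, "Participants will be advised to review the materials they received on nicotine withdrawal and proper use of NRT patches", with NRT discontinuation and referral to a physician if unmanageable symptoms persist. For category (c), the first step is in the session, and the next applies "If negative reactions to the mindfulness practice cannot be resolved within the group session by the trained mindfulness expert".

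Other relevant text:

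- Section 4 states that the trial is not blinded.
- Section 5 gives both arms six weeks of NRT. In Arm 1 it places the quit date at session 4 ("Will teach participants how cravings thwart long-term goals, and reinforce mindfulness techniques"), with eight sessions held twice weekly over four weeks.
- Section 5, Study measures, collects the CES-D and the Minnesota withdrawal scale (which covers anxiety and depression) at baseline and repeats them at 3 months.
- Section 7 (Data Management), which holds the analysis plan, compares pre/post differences between arms and explores improvement in depression. It plans no summary of adverse events.

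**The concern.** Categories (a) and (c) are separated by the cause that someone assigns, not by anything observed. New anxiety or low mood after the quit date meets category (a) on its face, and it could equally be a reaction to mindfulness practice. Section 9 gives no criterion, timing rule or assessor for the choice, and whoever makes it knows the arm.

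Category (c) is the only MT-specific harm that the protocol names. It can arise only in someone exposed to MT, so in Stage 1 it has no counterpart in the contingency management (CM) arm. If ambiguous symptoms tend to be called withdrawal, the count under (c) falls short, and the missing events appear as extra withdrawal symptoms in the MT arm. Only a table by symptom and arm would show that excess, and none is planned. A pilot meant to decide what to carry forward would then say less than it could about the tolerability of MT.

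The label also determines which follow-up instruction applies, so one presentation can fall under two.

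**Working it through.** There is no figure in the plan to reproduce: the documents give no adverse event rate and no calculation tied to safety. The check is a reading of the sections together, followed by an illustration with assumed rates.

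**1. Where the categories overlap.** Session 4 of 8 is the quit date, so 8 − 4 = 4 sessions (5 to 8) follow it. At two sessions a week that is 4 / 2 = 2 weeks of MT alongside early abstinence. Sessions 1 to 3 precede quitting, so a reaction then is not readily filed as quit-related withdrawal.

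**2. Which categories can arise in which arm (Stage 1).**

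| Category | MT | CM |
|---|---|---|
| (a) withdrawal | yes | yes |
| (b) patch effects | yes | yes |
| (c) mindfulness reaction | yes | no |

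In Stage 2, (c) can also arise in CM non-responders who are switched to MT.

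**3. How far misfiling could empty category (c).** Inputs: n = 50 MT participants (section 15); true reaction rate p and share m filed as withdrawal, both assumed. The rate seen under (c) is q = p(1 − m), and P(no case under (c)) = (1 − q)^50.

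| m | p = 10%: q | P(0) | p = 5%: q | P(0) |
|---|---|---|---|---|
| 0 | 0.100 | 0.5% | 0.050 | 7.7% |
| 50% | 0.050 | 7.7% | 0.025 | 28% |
| 80% | 0.020 | 36% | 0.010 | 61% |
| 90% | 0.010 | 61% | 0.005 | 78% |

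Step 1 limits which rows are realistic. If reactions were spread evenly over the eight sessions (an assumption), 4/8 = 50% would fall after the quit date, and the 50% row would be about the worst case. The 80% and 90% rows need reactions to be concentrated after quitting.

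**4. What a symptom table by arm could show.** Two-sided α = 0.05, 50 per arm, rates p1 and p2 assumed, p̄ their mean:

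power = Φ[(|p2 − p1| − 1.96 √(2p̄(1 − p̄)/50)) / √((p1(1 − p1) + p2(1 − p2))/50)].

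For 20% versus 30%: (0.100 − 1.96 × 0.0866)/0.0860 = −0.81, so power is 21%. Over background rates of 20%, 30% and 50%, power is 17–21% for a 10-point excess and 53–59% for a 20-point excess. The table would be descriptive.

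**5. Whether the scales fill the gap.** The CES-D and the Minnesota scale need no attribution and are taken in both arms. The 3-month visit repeats all baseline assessments except demographics. For the end-of-treatment visit, section 5 is inconsistent: the text after the study figure makes it the same as the 3-month assessment, while the itemised list for that visit omits both scales. At 3 months some non-responders will have switched intervention, which blurs the Stage 1 contrast.

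**The case against.** The best case against this point is that little is lost. Events under either label enter the same database, so an anxiety event called withdrawal is still on record and could be counted by arm. The CES-D and the Minnesota scale give a between-arm comparison free of staff judgement, and section 7 plans to compare pre/post differences between arms. Safety is neither a stated objective nor a listed outcome measure. Section 9 presents its list as events that may occur, and it foresees mindfulness reactions being handled in the session, where a trained person can see the context.

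Much of this stands, and it rules out several stronger readings:

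- A reader might infer that the protocol calls anxiety and depression unexpected when mindfulness causes them. It does not. Category (c) names no symptoms, and the overlap is a reasonable inference.
- A reader might infer that an MT harm signal would be hidden, or that the MT count would be near zero whatever the truth. The shared database and the pre-quit sessions argue against both.
- A reader might infer that the pilot cannot say whether MT adds psychological harm. The scales offer a partial answer.
- A reader might infer that only withdrawal events can arise in Stage 1 CM. Patch effects apply there too.
- A reader might treat CM as a clean control for symptom counts. Contact differs: twice-weekly sessions plus weekly calls in MT, against three contacts a week for three weeks in CM.
- The two follow-up routes need not conflict outright, since both can lead to the participant's physician.

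What remains is that recovering counts depends on symptom, severity and onset being stored, and the documents do not say they are. The scales are taken at one or two follow-ups and can miss transient reactions, and the analysis plan names improvement in depression but not anxiety. Section 9 also does not say which instruction governs a symptom that fits both categories.

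**Conclusion.** The point holds as one about under-counting. Cause-based categories, an overlap in time over half of the MT sessions, no blinding, no attribution rule and no planned table by arm together mean that a post-quit psychological symptom in an MT participant can be filed under either heading, and that mindfulness reactions may be under-recorded. It does not hold as a claim that harm would be concealed or could not be assessed.

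The size is unknown, because the documents give no rates. Under the assumed 5–10% reaction rates, filing half of the reactions as withdrawal raises the chance of an empty category (c) from 0.5–7.7% to 7.7–28%. More extreme figures need misfiling of 80% or more, which the session timeline makes less likely unless reactions cluster after quitting. The abstinence outcome is unaffected. This is an inexpensive improvement to safety recording and reporting.

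**What to change.** 1. In both arms and both stages, record each psychological event by symptom, severity and onset date relative to the quit date and, where applicable, to the last MT session. Ask the same symptom question at existing contacts in each arm.
2. Keep the staff view of cause as a separate field that does not decide whether or where an event is counted.
3. Add to section 7 a descriptive table of all such events, regardless of presumed cause, by randomised arm and by intervention being received at onset. Note beside it that contact frequency differs by arm.
4. Reconcile the follow-up instructions for categories (a) and (c) in section 9 for a symptom that fits both. The choice is a clinical one for the investigators.
5. Make the two descriptions of the end-of-treatment assessment in section 5 agree on whether the CES-D and the Minnesota scale are included, so that it is clear whether the attribution-free check exists at that visit.

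The cost is a few database fields, one standard question at contacts that already take place, and one table. More events will be listed in both arms, and the sample is too small for a formal test of the difference.

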3) Inclusion and Exclusion Criteria***A. Inclusion Criteria**

To be eligible participants should:

- Diagnosed with HIV (based on self-report).
- Be 18 years and older
- Have smoked ≥ 5 cigarettes/day in the past year

- Be interested in making a quit attempt in the next 30 days
- Own a smartphone (apple/android), and plan to keep it active for the next 6 months
- Able to consent
- Have no plans to move in the next 6 months
- Are not pregnant or planning to be pregnant in the following 6 months
- Have any condition that, in the opinion of the investigator, would compromise the well-being of the patient or the study or prevent the patient from meeting or performing study requirements

B. Exclusion Criteria

Participants would be excluded if they:

- Have contraindication to NRT (past month myocardial infarction, history of serious arrhythmias/or unstable angina pectoris, dermatological disorder)
- Are currently being treated for a psychiatric condition.
- Are currently being treated for smoking cessation, alcoholism, or illicit drug use
- Are adults unable to consent
- Are individuals who are not yet adults
- Are pregnant women
- Are prisoners

4) Study Design

- a. Study Type – Interventional
- b. Primary Purpose – Other
- c. Interventional Study Model – Sequential
- d. Number of Arms – 2
- e. Randomized or not – Randomized
- f. Open label or if blinded – Not blinded
- g. Number of participants – 100

5) Procedures Involved*

We will recruit participants via community and clinic flyers and among participants of another on-going survey who smoke (IRB#20180269). In Stage 1, participants will be randomized into one of two groups: 1) a group mindfulness training (MT) for smoking cessation, or 2) contingency management (CM) for smoking cessation. In Stage 2 non-

responders (those who have not quit at 1 month evaluation) will be randomized to: 1) *Switch* to sequentially receive the other intervention (i.e., CM or MI) and complete the 3-month assessment; or 2) *Continue* without further intervention and complete the 3-month assessment only.

In stage 1, both groups will do the following:

- Complete a baseline survey.
- Receive 6 weeks of Nicotine Replacement Treatment (NRT) via mail
- Receive reminder/encouragement calls or texts the day before their quit date and 2 weeks after their quit date.

Arm 1: The MT smoking cessation intervention:

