- f. *Session (6):* Will explore the automaticity of thought, and how thoughts can lead to habitual behaviors.
- g. *Session (7):* Will reinforce the concept of acceptance and its role in changing habits. It will also explore how both mental and physical actions can “plant seeds” for future actions and habits.
- h. *Session (8):* Will summarize the course tools and explore ways of maintaining these in the future. Home practice will be suggested after each session as a combination of formal MT meditations (the “body scan” which teaches individuals to systematically pay attention to different parts of their bodies as a way to reduce habitual mind-wandering and strengthen their attentional capacities, loving-kindness, and awareness of breath, which through focused attention on the breath also is intended to help individuals retrain their minds from habitually engaging in self-related pre-occupations -such as thinking about the past or future, or reacting to stressful stimuli- to more present moment awareness), and informal practices (four modes of walking, mindfulness of daily activities, mindfulness of smoking, RAIN). Participant will receive meditation recordings to practice.

[figure not shown]
Participants will receive a weekly phone call to ask a few questions on their use of the mindfulness practices taught in the sessions. This will take about 5 minutes.

Participants will receive \$20 for completing the baseline assessment, \$10 for attending each of the 8 sessions, \$10 for the end of the treatment assessment, and \$25 for the 3-month follow up assessment (a total of \$135).

Arm 2: Contingency Management (CM) Smoking Cessation Intervention

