Participants in this arm will attend an orientation session via Zoom that will last 60-90 minutes. They will connect with a research associate 3 times per week for 3 weeks after quit date via zoom where they will answer a few questions about their quitting progress, report on past 7-day smoking, and provide a sample of CO to verify their smoking status after their quit date using a portable CO monitor (coVita iCO™ Smokerlyzers®) and/or NicoTests saliva screen test that has been mailed to them. Those who proved their abstinence (CO< 8 ppm using coVita iCO™ Smokerlyzers®) and/or 30 ng/mL using NicAlert) [14] will receive a cash reward. The first successful CO sample earns \$5 cash, and then the reward increases by \$2 for each consecutive successful CO and/or saliva sample (e.g., \$5, \$7, \$9...). Participants also earn \$2 bonus for 4 consecutive successful CO and/or saliva samples (total=\$4). In all, participants can earn a maximum of \$176. Participant who fail the CO and/or saliva test will not receive reinforcement and the value of the next payment will be reset to the one that was missed.

Figure (1): overview of the study design

All participants will be asked to complete an end of treatment assessment 2 weeks after the intervention ends, which will be the same as the 3-month follow-up described below. Breath CO and/or saliva sample test (for cotinine analysis) will be collected at the end of treatment assessment via Zoom for participants who report they have quit.

All participants will be asked to complete a follow-up assessment 3 months after their quit date to assess their smoking status as well as get information about concomitant smoking and NRT use, use of additional NRT or cessation drugs (e.g., bupropion), and use of other tobacco methods. Breath CO and/or saliva sample test (for cotinine analysis) will be collected at the 3-month follow-up points for participants who report abstinence. The breath sample will be collected with the portable CO monitor (coVita iCO™ Smokerlyzers®) and/or NicoTests saliva screening test. A cut-off of 8 ppm for CO test (using coVita iCO™ Smokerlyzers®) and/or ≤ 30 ng/mL for the saliva sample test (using NicoTests) will be used to determine abstinence (Benowitz et al 2002).

Study measures

1. Baseline Assessment: All study materials and instrument will be translated into Spanish.

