- *Demographics and HIV history:* Age, race/ethnicity, birth origin, years in USA, relationship status, education, employment, income, acculturation, discrimination, self-identity, time since HIV diagnosis, HIV treatment.

Smoking status will be verified using breath carbon monoxide (CO [< 8 parts per million (ppm)], which can be determined quickly through a small, hand-held monitor and/or using a saliva screening test (cutoff concentration of ≤ 30 ng/mL), which can be determined quickly through a NicoTests saliva sample.

- *Smoking:* Smoking history, past quit attempt, motivation to quit, confidence in quitting, Fagerström test for nicotine dependence,^[15] 12-item smoking self-efficacy to resist urge to smoke,^[16] and 15-item Minnesota nicotine withdrawal scale (i.e., craving, irritability, anxiety, depression).^[17]

- *Mindfulness skills:* The 15-item short form five facets of mindfulness questionnaire that measures MT skills related to observing, describing, acting with awareness, non-judging of inner experience, and non-reactivity to inner experience.^[18]

- *Others:* The 20-item Centers for the Epidemiologic Study of Depression (CES-D) scale,^[19] social support,^[20] quality of life,^[21] and alcohol and substance use (ASSIST).^[22]

2. End-of treatment assessment (one month after quit date):

- The follow up assessment will occur at 1 months after quit date. The visit will last approximately 45 minutes.

- Information on number of sessions that was attended.

- *Acceptability:* The acceptability will be assessed by 3 items “How satisfied were you with the intervention?”, “How likely are you to recommend this intervention to a friend?” and “How useful was the intervention?”

Smoking Cessation: Main smoking cessation outcome is 7-day point-prevalence abstinence (defined as self-report of not smoking in the past 7-days; not even a puff) and confirmed smoking cessation by expired carbon monoxide (CO) level cutoff of < 8 ppm using a coVita iCO™ Smokerlyzer® and/or NicoTests saliva sample of ≤ 30 ng/mL at the 1-month follow up. Secondary outcomes include the reduction in number of cigarettes smoked per day.^[23,24] Relapse is defined as smoking at least once/week on two consecutive weeks.^[25] These are described in more detail below.

3. Three-month Follow-up Assessment (3-month after quit date):

- The follow up assessment will occur at 3 months (+30 days) after quit date. The visit will last approximately 45 minutes.

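### No scheduled contact is described as asking about patch reactions, mindfulness reactions or serious adverse events, so these may be under-recorded and captured unequally between Switch and Continue

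*Combined protocol and SAP*

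**What the plan says.** Section 9 lists two kinds of expected adverse event, nicotine withdrawal symptoms and side effects of the patches, and one unexpected kind, negative psychological reactions to mindfulness practice. Of the first two it says "These expected AE will be recorded in the participant tracking database", with a matching statement for the third. It gives no schedule, question, look-back period or form for finding them.

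The contacts at which such events could come to light are described in Section 5:

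- Both arms: "Receive 6 weeks of Nicotine Replacement Treatment (NRT) via mail", and a reminder or encouragement call or text the day before the quit date and two weeks after it.
- MT arm: eight group sessions over four weeks, and "Participants will receive a weekly phone call to ask a few questions on their use of the mindfulness practices taught in the sessions".
- CM arm: three video contacts a week for three weeks, at which participants "answer a few questions about their quitting progress, report on past 7-day smoking" and give a breath or saliva sample.
- End-of-treatment visit: "The follow up assessment will occur at 1 months after quit date". Section 5 also places it two weeks after the intervention ends, and the primary outcome timeframe places it at 4 weeks.
- Last visit: "The follow up assessment will occur at 3 months (+30 days) after quit date".

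In Stage 2, Continue participants receive no further intervention and have only the 3-month assessment.

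**The concern.** A rule that events are recorded works only if someone hears of them. Delivery is largely remote: NRT is mailed, and assessments are by video. No physical examination is described, so a rash or a new medical condition would surface only if the participant raised it. The responses in Section 9, such as giving advice or referring to a physician, also depend on staff knowing of the event.

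Two things are at stake. A low count of patch reactions or SAEs could not be told apart from a failure to ask. And the second randomization, Switch against Continue, sets a group with repeated staff contact beside one with none until the last visit. With passive reporting, any safety summary by that randomization would partly reflect the number of opportunities to speak. That cannot be repaired at analysis.

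**Working it through.** **What each contact asks, set against the Section 9 categories**

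| Contact | Stated content | Withdrawal or mood | Patch reaction | Mindfulness reaction | SAE |
|---|---|---|---|---|---|
| Reminder calls or texts | encouragement | no | no | no | no |
| MT weekly calls | use of mindfulness practices | no | no | no | no |
| CM check-ins | quitting progress, smoking, sample | no | no | no | no |
| End-of-treatment visit | described in Section 5 as the same as the 3-month visit | yes | no | no | no |
| 3-month visit | baseline battery without demographics, acceptability, smoking, NRT use | yes | no | no | no |

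The withdrawal and mood entries rest on the 15-item withdrawal scale and the 20-item CES-D in the baseline battery. The 3-month visit asks about use of NRT, but no question on reactions to it is listed. Section 9 does have the instructor deal with mindfulness reactions that arise within a group session, but that is a response and not a question put to everyone.

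**NRT supply against the end-of-treatment visit**

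The supply is 6 × 7 = 42 days, and its start is not stated. Counting from the quit date, the stated visit timings give:

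- 4 weeks: day 28.
- 1 month: about day 30.
- Two weeks after the intervention, CM: 3 weeks + 2 weeks = day 35.
- Two weeks after the intervention, MT: the quit date is session 4 of 8 at two a week, so about 2 weeks remain; 2 weeks + 2 weeks = about day 28.

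Days of NRT after the visit = (start day + 42) − visit day, or zero if negative:

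| Assumed NRT start | NRT ends | Visit day 28 | Visit day 30 | Visit day 35 |
|---|---|---|---|---|
| Quit date | day 42 | 14 | 12 | 7 |
| 1 week earlier | day 35 | 7 | 5 | 0 |
| 2 weeks earlier | day 28 | 0 | 0 | 0 |

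With a quit-date start, the overrun is 7/42 = 17% to 14/42 = 33% of the supply. The 3-month visit, at day 90 to 120 in 30-day months, then comes 90 − 42 = 48 to 120 − 42 = 78 days after the last patch.

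**Contacts**

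- Stage 1, MT: 1 orientation + 8 sessions + 4 weekly calls + 2 reminders = 15.
- Stage 1, CM: 1 orientation + 3 × 3 check-ins + 2 reminders = 12, or 15 with the 12 check-ins named in the adherence outcome.
- Stage 2, Switch to CM: 9 check-ins (12 by the adherence outcome).
- Stage 2, Switch to MT: 8 sessions + 4 weekly calls = 12.
- Stage 2, Continue: 0 intervention contacts before the 3-month visit.

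The Stage 2 counts assume that the Stage 1 format is repeated; no separate Stage 2 timetable is given.

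**The case against.** The strongest reply is that the trial is low risk and that more is asked than a quick reading suggests. The patches are sold over the counter, participants are screened for conditions that preclude them, and education on side effects is promised. Withdrawal symptoms are a listed adverse event category, and the withdrawal scale and CES-D cover part of it in every arm at both follow-ups. Participants may also volunteer a reaction. The few questions at the MT and CM contacts are not reproduced, and the consent pages are not available, so an adverse event script may exist elsewhere. All of this stands. It narrows the point to patch reactions, mindfulness reactions and SAEs, and makes the consequence possible under-recording, not certain loss.

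Four stronger readings are tempting, and the documents do not support them:

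- *Late patch reactions will be missed.* The overrun depends on an unstated start date and disappears with a start two weeks before the quit date. Contacts for responders after month 1 are not described, and Section 15 mentions follow-up reminders by text, mail or email, so complete silence until month 3 is not established.
- *Adverse event counts will be biased between MT and CM.* Stage 1 contacts are similar, 15 against 12 to 15.
- *A planned safety comparison is invalid.* No between-arm adverse event comparison is planned in Section 7, and no listed outcome is a safety outcome. Nor do the documents give a chance of spontaneous mention per contact, so the size of any detection difference cannot be calculated.
- *The tracking database contradicts Section 7*, which says "All study data will be entered and captured by REDCap". Nothing places the tracking database outside REDCap.

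**Conclusion.** The point holds in this limited form. As written, the plan captures patch reactions, mindfulness reactions and SAEs passively. They may be under-recorded, and the opportunity to report them differs in Stage 2: about 9 to 12 further intervention contacts for Switch against none for Continue before the 3-month visit. That contrast assumes that Switch repeats the Stage 1 format.

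For NRT starts between two weeks before the quit date and the quit date itself, 0 to 14 of the 42 patch days fall after the end-of-treatment visit; a quit-date start gives 7 to 14. The primary abstinence outcome is not affected. This is an inexpensive improvement to safety capture in a low-risk pilot, worth making because events that were never asked about cannot be recovered later.

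**What to change.** Add one fixed adverse event item set to three contacts that every participant already has: the 2-week call or text, the 1-month visit and the 3-month visit. The items would be:

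- skin or patch reaction;
- reaction to mindfulness practice;
- new onset of a condition listed in Section 3B ("past month myocardial infarction, history of serious arrhythmias/or unstable angina pectoris, dermatological disorder");
- any hospital visit;
- one open question.

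Use the same wording and look-back period in every arm, including responders and both Stage 2 groups. At the 3-month visit the look-back should cover all time since the 1-month visit, including the rest of the NRT supply. Base any adverse event summary by arm, or by Switch against Continue, on these common-schedule items, and list spontaneous reports separately. The plan should also state when NRT starts and reconcile its end-of-treatment visit timings, so that the look-back can be defined.

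The cost is about five questions, one or two minutes per contact, and a higher recorded count, which should be expected when the results are read. One limit remains. With the 1-month visit at day 28 to 35, the 3-month look-back runs from 90 − 35 = 55 to 120 − 28 = 92 days, so mild events may be forgotten, but the question and period will be the same for Switch and Continue.
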